### **6.2 Post-operative Application of Surgical Site Adhesive**

After the completion of the surgical procedure the surgical site will be prepared in a standard fashion using appropriate layered closure. During this time, the products (Opticlose or Dermabond), will be applied to the surgical site incision. Following the application of the products, the time the products take to dry on the surgical site will be recorded using a stopwatch.

For the mesh group, the stopwatch will begin when the package is opened and once the mesh is laid down for initial application. Once the mesh is appropriately applied, the first time stamp will be recorded. The stopwatch will begin again once the glue has been opened and will stop once the glue has sufficiently covered the mesh for a second time stamp. The stopwatch will then start again, and the applicator will touch the application site at 15 second intervals until no glue is detected on the gloved finger. Once dry, the third and final time stamp will be recorded.

For participants assigned to the glue only group, the stopwatch will begin once the glue has been opened and will stop once the target area has been sufficiently covered for the first time stamp. The stopwatch will begin a second time and the applicator will touch the application site at 15 second intervals until no glue is detected on the gloved finger. Once dry, the second time stamp will be recorded.

The number of applicator tubes used when applying the various products will also be recorded during the product application.

Throughout this process, the circulating nurse will be assessing the participants for potential adverse events related to any surgical site infections or any signs of allergic skin

reactions. If an allergic reaction is detected the assessment will include an International Contact Dermatitis Research Group (ICDRG) grading system (see appendix). Following the completion of the assessment, the participants will be allowed to leave and follow up in their next office visits.

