## **6. STUDY PROCEDURES AND ASSESSMENTS**

### **6.1 Participant Screening and Informed Consent**

The pre-visit may take up to 30 minutes. Study staff will screen potential participants and obtain informed consent during this time as described in Section 5.

Participants will be randomized depending on the predicted incision size. If the incision site is large enough to require the use of the mesh and glue combination, participants will be randomized into the OptiClose Secure group or the Dermabond Prineo group. If the incision site is determined to be small enough that it does not require a mesh, participants will be randomized into the OptiClose Rapid group or the Dermabond Advanced group.

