### **8.2 Randomization**

The order of products tested first or second will be randomly assigned according to a randomization table developed by the biostatistics team. We will conduct a two-arm, prospective, unblinded, randomized prospective control trial by which participants will be randomly assigned to either receive treatment A: the Dermabond wound closure adhesive or the treatment B: OptiClose wound closure adhesive in participants undergoing the closure of any subcutaneous tissue following surgical site incisions. After assignment to treatment arm per incisional length requirements, participants will be randomized using

simple randomization, with 15 participants designated to receive Opticlose and 15 to receive Dermabond. Participants will be patients undergoing a skin closure of a full thickness surgical incision. For the products tested in this study, a total of 60 participants will be required to complete the study, 30 in each incisional length group. If a participant is unable to complete the study, the participant will be replaced such that the new participant will be assigned to the randomization cohort of the replaced participant.

Enrollment will continue until the study from the evaluable number of participants (60) is completed.

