### **8.5 Demographics, Variables and Covariates**

Age will be collected as a continuous measure, with all participants being  $\geq 18$  years of age. Age strata will be defined as stratum 1: 18-25 years old, stratum 2: 26-41 years old, stratum 3: 42-57 years old, stratum 4: 58-67 years old, stratum 5: 68-76 years old, stratum 6: 77-94 years old, 95+ years old. Age will be considered for secondary analysis.

Sex will be collected as a categorical equal to 0=male and 1=female. Sex will be considered for secondary analysis.

Race/Ethnicity has been requested by the division as a covariate and will be considered for secondary analysis.

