### **Number of Applicator Tubes**

- A Chi-Square test will be used to compare the observed frequencies of number of tubes between the two products. The test statistic is calculated by comparing the observed frequency to the expected frequency under the null hypothesis. The p-value will be obtained to determine the statistical significance of the observed difference.

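### Actual incision length is not recorded, so a chance difference in length between products cannot be seen or adjusted for in tube count and coverage time

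*Combined protocol and SAP*

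**What the plan says.** Incision size enters the plan once. Section 6.1 states "Participants will be randomized depending on the predicted incision size", meaning a mesh-plus-glue group and a glue-only group. Section 8.2 then allocates product within each group by "simple randomization, with 15 participants designated to receive Opticlose and 15 to receive Dermabond". The eligibility criteria in the synopsis set no limit on incision length, and no threshold in centimetres separates the two groups.

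Three quantities are recorded at application (6.2):

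- **Tubes:** a raw count, in the words "The number of applicator tubes used when applying the various products will also be recorded during the product application".
- **Coverage time:** in the glue-only group the stopwatch "will stop once the target area has been sufficiently covered for the first time stamp". In the mesh group there is a separate mesh time, and the glue stopwatch "will stop once the glue has sufficiently covered the mesh for a second time stamp".
- **Touch-dry time:** the stopwatch restarts after coverage, and "the applicator will touch the application site at 15 second intervals until no glue is detected on the gloved finger".

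The covariates in 8.5 are age, sex and race/ethnicity; of the last it says "Race/Ethnicity has been requested by the division as a covariate and will be considered for secondary analysis". Measured incision length appears neither there nor in the schedule of activities (1.2).

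For tubes, 8.8.2 says "A Chi-Square test will be used to compare the observed frequencies of number of tubes between the two products". For times, it plans a between-group comparison of dry time only. Total time with its glue, mesh and dry components is summarised by mean and SD. Neither entry says that the mesh and glue-only groups are analysed separately. Section 8.8.3 plans no supplemental analyses.

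**The concern.** Two of the recorded quantities are tied to the size of the wound by the way they are measured. Coverage time ends when the area or mesh is covered, and the number of tubes opened depends on how much there is to cover. The secondary objectives use these quantities to describe the products. If one product happens to be used on longer incisions, it will tend to need more tubes and more time for reasons unrelated to the product.

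Without a length measurement, a reader cannot tell whether that happened, and the analyst cannot correct for it. Nor can anyone check afterwards that the predicted mesh/no-mesh split matched the wounds actually closed. Photographs will not fill the gap: under 6.5 they are optional, need not cover everyone and are excluded from statistical comparison. Even with perfect balance, variation in length within a group adds noise to the tube-count comparison.

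**Working it through.** **Inputs.** From 8.1 and 8.2: n = 15 per product within each incision-length group, one-sided alpha 0.025, 90% power. The correlation r between incision length and the outcome within a group is not in the documents. It is an assumption, shown from 0 to 0.7.

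**The plan's own figure.** Section 8.1 gives a detectable difference in mean dry time of 0.02226 for SD 0.01. With a null difference of zero, the noncentral t (28 df) gives 0.01226, or 1.226 SD. Since 0.01226 + 0.01 = 0.02226, the stated figure fits a calculation with an unstated margin of 0.01. That is a separate matter about dry time. Here 1.23 SD serves only as the unadjusted benchmark for 15 v 15.

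**Step 1: chance imbalance in length.**
SE of the difference in mean length = sqrt(1/15 + 1/15) = sqrt(2/15) = 0.365 SD of length.
95% range = ±1.96 × 0.365 = ±0.72 SD.
P(gap > 0.5 SD) = 2 × [1 − Φ(0.5/0.365)] = 2 × [1 − Φ(1.369)] = 0.17.
By the same formula, P(gap > 0.75 SD) = 4.0% and P(gap > 1 SD) = 0.6%.
With 30 per product (both groups together, imbalance in within-group SD units), SE = sqrt(2/30) = 0.258 and P(gap > 0.5 SD) = 5.3%.

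**Step 2: what a 0.5 SD gap does.** It shifts the product difference by 0.5 × r outcome SDs.

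**Step 3: false positives.** 40,000 trials were simulated for each r with no product effect, normal outcomes, 15 v 15 and an unadjusted unequal-variance t-test at two-sided 0.05.

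**Step 4: gain from adjustment.** Under ANCOVA with length, the residual SD is sqrt(1 − r²), the df are 27, and the SE is sqrt(2/15) × sqrt(1 + 1/26) × sqrt(1 − r²). The factor sqrt(1 + 1/26) is the average cost of estimating the slope.

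| Assumed r | Shift from 0.5 SD gap (outcome SD) | Type I error, all trials | Type I error, trials with gap > 0.5 SD | Detectable difference, unadjusted (SD) | Detectable difference, adjusted (SD) |
|---|---|---|---|---|---|
| 0 | 0 | 0.048 | 0.05 | 1.23 | 1.25 |
| 0.3 | 0.15 | 0.049 | 0.07 | 1.23 | 1.19 |
| 0.5 | 0.25 | 0.049 | 0.11 | 1.23 | 1.08 |
| 0.7 | 0.35 | 0.048 | 0.17 | 1.23 | 0.89 |

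The fourth column describes the minority of trials with a visible imbalance, which this trial could not identify. Steps 3 and 4 treat the outcome as continuous. For a small integer such as tube count they are a guide to size, not exact.

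**The case against.** The strongest reply is that randomisation already deals with this. Product is allocated within the mesh and glue-only groups, so length is balanced in expectation, and the standard error of an unadjusted comparison already contains the chance imbalance. The simulation agrees: type I error over all trials is 0.048 to 0.049 whatever the correlation. A reader might infer that product and incision length are confounded. The documents do not support that. Two features weaken the protection of randomisation: 8.3 limits the analysis set to participants with complete data, and 8.2 replaces those who do not finish. Nothing suggests, however, that either acts through incision length.

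A reader might also infer that the dry-time comparison, on which the sample size rests, is compromised. That is not shown either. Touch-dry time is a separate interval started after coverage is complete, and no passage links it to length. Glue and mesh times, which plausibly do scale with length, are summarised and not tested. Tube count is therefore the only outcome that is both plausibly length-dependent and formally compared.

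Three further points stand in part:

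- The mesh split removes some variation, and both mesh products are listed at 22 cm in 2.2, which may narrow the spread in that group. This does nothing for the glue-only group.
- The correlations are assumed. At r = 0.3 the gain is slight, and an integer tube count with few distinct values may not correlate strongly with length.
- Length at closure is measured after allocation in an unblinded trial. Taken before the product is applied, it cannot be influenced by how the product performs.

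What the objection leaves untouched is that randomisation neither restores lost precision nor lets anyone inspect the one trial that is run.

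**Conclusion.** The point holds as one of precision and interpretability in the secondary outcomes. Actual incision length is neither recorded nor used, while tube count and coverage time plausibly depend on it. At 15 v 15 a gap in mean length above 0.5 SD arises by chance in about one trial in six and would go unseen. The plan thereby forgoes a reduction in detectable difference of about 12% at r = 0.5 (1.23 to 1.08 SD) or 27% at r = 0.7 (1.23 to 0.89 SD). If length proved unrelated, adjusting would cost about 2% (1.23 to 1.25 SD).

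The imbalance figures need only the planned sample size and approximate normality of the mean difference in length. The precision figures rest on the assumed correlations and a continuous outcome. The effect falls on the tube-count comparison and on the reading of the descriptive application and total times. The primary endpoint is not involved.

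**What to change.** 1. **Schedule of activities, Post Op column, and 8.5:** add actual incision length in cm, measured at closure before product application.
2. **8.8.2, Number of Applicator Tubes:** replace the unadjusted chi-square with a comparison within, or stratified by, mesh/no-mesh group, using a count or ordinal model with length as covariate. Replacing the test, rather than adding one, keeps the number of secondary comparisons unchanged.
3. **8.8.2, Dry Time:** if application or total time is to be compared between products, use ANCOVA with length within the same groups. Otherwise keep these times descriptive.
4. **Reporting:** tabulate incision length by product within each group. Per-cm figures should be descriptive only. A tube is opened whole, so tubes per cm falls with length inside a single tube whatever the product.

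The cost is one ruler reading, one CRF field and one degree of freedom. The gain depends on a correlation that is not yet known and is small if that correlation is low.

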### **6.3 Follow-up post-operative visit (Visit 2 & 3)**

In the second and third post-operative visits, the incisional wounds will be assessed for possible dehiscence and the results will be recorded. Moreover, an incisional site cosmetic score will be obtained using the Modified Hollander score for linear scars and will be used to further assess and categorize the current wound state. As with the first visit, the research staff will also assess any potential adverse event that may have resulted from the use of the topical adhesives. Additionally, any incidence of surgical site infections will be noted. Following the assessments during the third visit, the participants will be dismissed from the study. The CDC SSI and ICDRG grading systems will be used if either of the two events are deemed applicable by the study staff.

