**Endpoints:**

*Primary Endpoint:* Incidence of wound edge apposition without dehiscence or need of re-approximation following wound closure.

*Secondary Endpoint:* Secondary endpoints include:

- Surgical Site Infections (SSIs) (criteria defined by the CDC), if applicable
- Inflammatory reactions as calculated by the International Contact Dermatitis Research Group (ICDRG) grading system (see appendix), if applicable.
- Cosmesis as assessed by the Modified Hollander score (see appendix).
- Dry time as objectively measured by an observer/end user.
- Number of applicator tubes/mesh used.

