**1.2. Schedule of Activities (SOA)**

	Pre-Op	Post Op	Post Op Follow Up 1	Post Op Follow Up 2
Informed Consent/Subject Enrollment	x			
Product Application to surgical site		x		
Dry time recording (with stopwatch)		x		
Number of applicator tubes used		x		
Circulating Nurse notes assessment for adverse events related to allergic reactions. IF applicable, preforms the International Contact Dermatitis Research Group (ICDRG) grading system		x	x	x
Incidence of Surgical Site Infection (SSIs). If applicable performs the CDC criteria for SSI.		x	x	x

Incisional Site Wound Dehiscence Check (inspection of wound edge approximation).			X	X
Incisional Site Cosmesis Score Check using Modified Hollander Scale			X	X
Incisional Site Photos*		X	X	X
Subject Dismissal				X
*Only applies to participants who have consented to incisional site photos.				

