#### **Incidence of Surgical Site Infections**

The incidence of surgical site infections (SSIs) will be recorded for each subject (as occurring within 30 days of treatment). Descriptive statistics will include the total number of infections. Comparative analysis between treatment groups will be conducted using Chi-Square tests or Fisher's exact test if the expected frequencies are low.

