## 11. APPENDIX

Reaction	Definition
+?	Doubtful reaction; faint macular erythema only
+	Weak positive reaction; erythema, infiltration papules
++	Strong positive reaction; erythema, infiltration, papular, vesicles
+++	Extreme positive reaction; intense erythema, infiltration and coalescing vesicles
-	Negative reaction
IR	Irritant reaction
NT	Not tested

ID	Step-off of borders (Edges not on the same plane)	Contour irregularities (Wrinkled skin near the wound)	Margin separation (Gap between the sides)	Edge inversion (Wound not properly everted)	Excessive distortion (Swelling or infection)	Patient satisfaction score (1–10)	Operator satisfaction score (1–10)
A							
B							
C							
D							
E							

Is the overall appearance? ☐ Acceptable ☐ Not acceptable

For each wound, please answer Yes or No to each characteristic.

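### No recorded sign obliges staff to apply the CDC infection criteria, and a wound gap recorded on the cosmesis form can still count as a primary success

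*Combined protocol and SAP*

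**What the plan says.** **Infection.** The synopsis lists the endpoint as "Surgical Site Infections (SSIs) (criteria defined by the CDC), if applicable". The Schedule of Activities (1.2) puts infection incidence at all three post-operative time points and adds "If applicable performs the CDC criteria for SSI". Section 6.3 says of the follow-ups "Additionally, any incidence of surgical site infections will be noted", and then "The CDC SSI and ICDRG grading systems will be used if either of the two events are deemed applicable by the study staff". Section 8.8.2 says incidence "will be recorded for each subject (as occurring within 30 days of treatment"), to be compared by chi-square, or by Fisher's exact test when expected counts are low.

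**Cosmesis form.** The Modified Hollander check is scheduled at both follow-ups. The appendix form requires a Yes or No for each wound on several items, including "Excessive distortion (Swelling or infection") and "Margin separation (Gap between the sides"). Section 6.3 uses the score to describe the state of the wound, and Section 8.8.2 analyses it as cosmesis.

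**Dehiscence.** Wound edges are inspected at both follow-ups, unconditionally. No definition or threshold is given. The title of the primary endpoint names both dehiscence and re-approximation, but the counting sentence in 8.8.1 mentions only participants who did not need re-approximation.

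**Blinding.** Section 8.2 describes a "two-arm, prospective, unblinded, randomized prospective control trial". No blinded assessor or adjudication is described. Photographs are optional and excluded from statistical comparison (6.5).

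**The concern.** A standard case definition is there to decide whether a suspicious wound is an infection. Here staff first judge whether the event applies, and the definition follows. They may know the product, and no listed finding obliges them to open the criteria.

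The plan already collects two relevant findings on every wound at the same visits, but does not connect them to the endpoints they bear on. A swollen or infected-looking wound need not lead to the CDC criteria. A gap between the wound edges need not lead to an entry of dehiscence, or to any query when none is entered.

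The second gap in the plan reaches the primary endpoint. The stake is whether the primary and infection results agree with other data recorded at the same visit, and whether a reader could tell if they do not.

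**Working it through.** The plan gives no rate for infection or dehiscence, and its only sample-size figure concerns dry time. There is therefore no figure of the plan to reproduce on this point. The check is to follow a wound through the text, and then to see how sensitive the comparison is to single reclassifications.

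**Wound A: *Excessive distortion* is Yes at a follow-up.**
- Sections 1.2 and 6.3: staff note whether there is an infection. The CDC criteria follow only if they deem them applicable.
- Appendix and 8.8.2: the Yes enters cosmesis.
- No section makes the Yes a reason to complete the criteria. If staff do not open them, the participant has no infection in the analysis, and nothing shows whether the criteria would have been met.

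**Wound B: *Margin separation* is Yes and the wound is not re-approximated.**
- If dehiscence is also recorded, the endpoint title makes this a failure, but the counting sentence in 8.8.1 makes it a success.
- If dehiscence is not recorded, the wound is a success on either reading, and no rule asks why the two records differ.
- The test sentence in 8.8.1 speaks of adverse event frequencies, which does not settle what counts as failure.

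**Sensitivity to single reclassifications.** Inputs from 8.2: 60 participants, 15 per product within each incision-length group, hence 30 per product if pooled. The event counts below are assumptions, as is a two-sided 0.05 threshold.

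- Hollander forms: 60 × 2 = 120 at most. The endpoints are per participant, so this is a ceiling on forms and not on events.
- One participant: 1/15 = 6.7 points; 1/30 = 3.3 points.
- For k events against 0 with n per product, the uncorrected chi-square is 2nk/(2n − k), and two-sided Fisher p = 2·C(n,k)/C(2n,k).

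| n per product | k vs 0 | Chi-square | p (chi-square) | p (Fisher) |
|---|---|---|---|---|
| 30 | 3 | 180/57 = 3.16 | 0.076 | 0.237 |
| 30 | 4 | 240/56 = 4.29 | 0.038 | 0.112 |
| 30 | 5 | 300/55 = 5.45 | 0.020 | 0.052 |
| 30 | 6 | 360/54 = 6.67 | 0.010 | 0.024 |
| 15 | 3 | 90/27 = 3.33 | 0.068 | 0.224 |
| 15 | 4 | 120/26 = 4.62 | 0.032 | 0.100 |
| 15 | 5 | 150/25 = 6.00 | 0.014 | 0.042 |

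The expected count is k/2 per product, at most 3 here, so Fisher would be the likely test for infection; 8.8.1 names chi-square for the primary endpoint. With 30 per product, one participant takes the primary test across 0.05 between 3 and 4 events, and the infection test between 5 and 6. With a continuity correction the chi-square crossing also moves to between 5 and 6 (p = 0.062 and 0.031).

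**The case against.** The case on the other side is substantial, and most of it limits the point without removing it.

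- **Swelling is not infection.** A reader might infer that a wound can be recorded as infected on one form and infection-free in the endpoint. The documents do not support this: the item bundles swelling with infection, and swelling alone earns a Yes. A Yes is a signal to check, not an SSI.
- **Infection is looked for at every visit.** Only the formal criteria are conditional, so under-ascertainment is possible but not shown. Nor is the safety review starved of data: 6.3 requires adverse events from the adhesives to be assessed separately, and 8.8.4 reports all adverse device events.
- **Dehiscence inspection is not discretionary.** The conditional wording covers the CDC and ICDRG systems only. The gap half of the point rests instead on the missing definition and on the counting sentence in 8.8.1.
- **Same staff, same form.** The documents do not say that one person makes all the assessments or that they share one case report form.
- **Quality checks exist.** Section 9.1.1 provides for checks on inconsistent data. They are generic, and nothing identifies these pairs of entries as an inconsistency.
- **The arithmetic is generic.** It would hold for any misclassification in a trial of this size. Three one-directional calls starting from none shift the comparison by 3/30 = 10 points, yet p is 0.076 or 0.237.
- **The Hollander answers are unblinded too**, and the form is not scheduled at the immediate post-operative check. A trigger based on it limits discretion at the follow-ups only.

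**Conclusion.** The point holds as a cheap improvement, in two parts. First, the criteria that define the infection endpoint are applied at the discretion of staff in an unblinded trial, and no recorded sign makes them mandatory. Second, a wound with a recorded gap that was not re-approximated counts as a success under 8.8.1, although the endpoint title also requires freedom from dehiscence.

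No effect size can be given, because the documents state no infection or dehiscence rate. The tabulated counts are assumed. They show only that one participant can cross a significance threshold at these sample sizes, not that any result has been biased. The tempting conclusion that infections are being missed, or that the results are slanted towards one product, goes beyond the text.

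**What to change.** 1. In 6.3 and the Schedule of Activities, require the CDC criteria to be completed and the result recorded whenever *Excessive distortion* is Yes or infection is otherwise suspected.
2. Within the quality checks of 9.1.1, add a specific check that reconciles every Yes for *Margin separation* with the dehiscence record before database lock.
3. In 8.8.1, count recorded dehiscence as well as re-approximation as failure, in line with the endpoint title. Add a sensitivity analysis that counts any Yes for *Margin separation* as failure.

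Section 8.1 already speaks of reporting superiority results because non-inferiority was indeterminate. If data have been reviewed, label the changes in item 3 as post hoc. If the visits are over, items 2 and 3 can still be run on the recorded Hollander answers.

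The cost is some extra CDC form completions for wounds that prove merely swollen, one data check and one table, with no new visit. The sensitivity analysis is stricter than dehiscence and should be read as such. Because dehiscence is undefined, reconciliation shows where the records disagree, not which is right. None of this removes unblinded-assessor bias.
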